# 5.3.1 Post-Surgical Intraocular Inflammation

For the primary safety endpoint, the rate (per 1,000 IOL implants) of post-surgical intraocular inflammation (based upon the specified case definition) reported within a 180-day post-surgical period following attempted implantation of study IOLs (Cohort 2) in the United States will be estimated along with the exact two-sided 95% confidence interval. The event rate (per 1,000 IOL implants) is calculated as:

Total # of reported events/Total # of attempted implants x 1,000

An eye with multiple reports of inflammation is only counted once toward the total of the inflammation cases and the one related to device will take precedence. The inflammations related to the device will also be summarized. Event rates will be presented by first eye, second eye, and overall eyes, respectively. A subgroup analysis on the primary safety endpoint will be performed by age groups (22-64 years vs. 65 years or older). If both eyes of a subject are enrolled in this study, full follow-up information for both eyes will be used in the primary analysis.

As sensitivity analyses, cumulative event rates of post-surgical intraocular inflammation (based upon the specified case definition) at 180 days will be provided using Kaplan-Meier estimator for first eyes, second eyes, and overall eyes. The corresponding two-sided 95%

confidence interval of the rates will also be provided. Graphical presentations of the Kaplan-Meier post-surgical intraocular inflammation curves for overall eyes will be included. Kaplan-Meier estimators will be calculated using two different censoring rules as follows:

- 1. Full follow-up information for both eyes is used. If an eye does not have inflammation, then follow-up is censored at the time (days) from each surgery to the last known date in the study for each eye;
- 2. If a subject has a second cataract surgery within 180 days of the occurrence of the first cataract surgery, the follow-up for the first eye will be censored at the time of second surgery, in the case of no inflammation before the second surgery, for calculating rates for first eyes.

For secondary safety, the rates of Toxic Anterior Segment Syndrome, acute postoperative endophthalmitis, chronic postoperative endophthalmitis, and uncategorized cases of postsurgical intraocular inflammation (based upon the specified case definition) reported within a 180-day post-surgical period following attempted implantation of study IOLs (Cohort 2) in the United States will be estimated for first eyes, second eyes, and overall eyes along with the exact two-sided 95% confidence intervals. An eye with multiple same type of inflammation is only counted once toward the total of that type of inflammation and the one related to device will take precedence. An eye with multiple different types of inflammation is only counted once; the inflammation related to device will take precedence, otherwise the precedence will follow the sequence of TASS, acute postoperative endophthalmitis, chronic postoperative endophthalmitis, and uncategorized cases. Inflammations related to the device will also be reported. Cumulative event rates at 180 days will be provided using Kaplan-Meier estimator as described above for first eyes, second eyes, and overall eyes for the secondary safety endpoints as a sensitivity analysis.

A listing of eyes with all such primary and/or secondary events will be provided, where all multiple inflammations that occurred in one eye will be listed.

A listing of eyes with post-surgical intraocular inflammation and with a corneal edema grade greater than the lowest level (Grade 0 – no stromal or epithelial edema) will be provided.

Summary statistics for the rate (per 1,000 IOL implants) of post-surgical inflammation will be provided by presence of corneal edema for overall, first eyes, and second eyes.

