# 1.2 Study Description

This is a prospective, multi-center, active surveillance post-approval study designed to estimate the incidence of post-surgical intraocular inflammation (based upon a specific case definition) in approximately 3,300 eyes that have been implanted with an ACRYSOF IQ RESTOR Toric IOL or ACRYSOF IQ RESTOR multifocal IOL in the US (Cohort 2) for up to 180 days. Active surveillance will be conducted through systematic collection, analysis, and interpretation of all reported cases of post-surgical intraocular inflammation over 4 visits ranging from 1 to 180 days post implantation of the ACRYSOF IQ RESTOR Toric or ACRYSOF IQ RESTOR IOL. The ACRYSOF IQ RESTOR Toric IOL and ACRYSOF IQ

RESTOR IOL are commercially available in the United States. This study will include adults (≥ 22 years of age) with preoperative cataract in the study eye(s). Potential subjects will be screened for enrollment into the study. Those qualifying will be considered enrolled in the study at the time the informed consent form is signed and attend a total of up to 11 scheduled visits. The subject will be considered exposed to treatment at the time of surgery when the investigational product touches the eye.

The study includes two groups of subjects (Cohort 1 and Cohort 2).

Cohort 1: Subjects implanted from November 2018 through July 2020 with ACRYSOF IQ RESTOR +3.0 D Multifocal Toric IOL (Models SND1T3, SND1T4, SND1T5 or SND1T6) or an ACRYSOF IQ RESTOR +2.5 D Multifocal Toric IOLs (Models SV25T3, SV25T4, SV25T5, and SV25T6) in at least one eye.

Note: At time of Protocol Amendment 7, Cohort 1 enrollment is complete.

Cohort 2: Subjects implanted after July 2020 with ACRYSOF IQ RESTOR +3.0 D Multifocal Toric IOL (Models SND1T3, SND1T4, SND1T5 or SND1T6) or an ACRYSOF IQ RESTOR +2.5 D IOL (Model SV25T0) in at least one eye.

Note: This Cohort will include subjects enrolled under Amendment 7 and later.

An overview of the study design is depicted in Figure 7-1 of the protocol, and the schedule of visits is presented in Table 12-1.

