#### **5.3.2** Adverse Events

The applicable definition of an Adverse Event (AE) is in the study protocol. All AEs occurring from when a subject signs informed consent to when a subject exits the study will

be accounted for in the reporting. A treatment-emergent AE is an event not present prior to exposure to treatment or any pre-existing event that worsens following exposure to treatment. All information obtained on adverse events will be displayed by subject and eye.

The number and percentage of all ocular adverse events and the associated two-sided exact 95% confidence interval, including secondary surgical interventions (SSIs) for either eye, will be tabulated for any event and by preferred term with a breakdown by overall, first eyes, and second eyes. An eye with multiple ocular adverse events of the same preferred term is only counted once toward the total of this preferred term. Adverse events related to the study IOL are referred to as adverse device effects.

Adverse events will be summarized in tables with the following:

- 1. All Adverse Events (Serious and Non-Serious Combined)
  - a. Ocular
  - b. Non-Ocular
- 2. All Adverse Device Effects
  - a. Ocular
  - b. Non-Ocular
- 3. All Serious Adverse Events (including Serious Adverse Device Effects)
  - a. Ocular
  - b. Non-Ocular
- 4. Subject Listings
  - a. Non-Serious Ocular
  - b. Non-Serious Non-Ocular
  - c. Serious Ocular
  - d. Serious Non-Ocular
  - e. Pre-Treatment Adverse Events
  - f. Ocular Adverse Events from Non-Study Eyes
  - g. Secondary Surgical Interventions

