# 12 APPENDIX

 Table 12-1
 Schedule of Study Procedures and Assessments

Procedure/ Assessment	Visit 0 (≤ 40 days pre-surgery 1st eye, ≤ 60 days pre-surgery 2nd eye)	Visit 00 & Visit 00A (surgery)	Visit 1 & Visit 1A (Day 1-2 post surgery)	Visit 2 & Visit 2A (Day 7-14 post surgery)	Visit 3 & Visit 3A (Day 30- 60 post surgery)	Visit 4 & Visit 4A (Day 90 - 180 post surgery)	UNSV
Informed Consent	X						
Demographics	X						
Patient Medical History (Ocular and Nonocular) 	X						
Medications (use of medication prior to, during and post-surgery must be documented) 	X	X	X	X	X	X	X
Inclusion/ Exclusion	X	X					
Adverse Events (Volunteered and Elicited)	X	X	X	X	X	X	X
Device Deficiencies		X	X	X	X	X	X
Subject Reported Symptoms	X		X	X	X	X	X
Best Corrected Visual Acuity (BCVA)	X		X	X	X	X	X
Intraocular Pressure	X		X	X	X	X	X
Problems during surgery		X					
Other Surgical Procedures		X					
Aqueous cell	X		X	X	X	X	X
Aqueous flare	X		X	X	X	X	X
Corneal edema	X		X	X	X	X	X
Corneal haze	X		X	X	X	X	X

Fibrin in the anterior chamber, on the surface of the iris or on the intraocular lens (IOL)	X	X	X	X	X	X
Eyelid edema	X	X	X	X	X	X
Conjunctival hyperemia	X	X	X	X	X	X
Ciliary flush	X	X	X	X	X	X
Corneal precipitates	X	X	X	X	X	X
Hypopyon	X	X	X	X	X	X
Dilated fundus examination	X	X 				
Vitreous cell	X	$X^1$	$X^1$	$X^1$	$X^1$	$X^1$
Vitreous haze	X	X 	X 	X 	X 	X1
Photo documentation		$X^2$	X 	$X^2$	$X^2$	X 
Culture of ocular media		$X^2$	$X^2$	$X^2$	$X^2$	$X^2$

 Required for cases of exacerbated post-surgical intraocular inflammation only.

- Medical History: All ocular history, targeted systemic history
- Concomitant Medications: All ocular medications, targeted systemic medications

*NOTE*: Visits with an "A" refer to visits for the 2nd eye visits for cases where both eyes of a subject are enrolled. In the eCRF these visits will be noted with wording of "2nd Eye" instead of A. For example: Visit 1A will be shown as Visit 1-2nd Eye.

 Required at certain visits for cases of exacerbated post-surgical intraocular inflammation. See Manual of Procedures for details on requirements for which visit(s) testing is required.

 Concomitant medications and medical history must be fully documented in the subject source documents. CRF data will be Targeted:

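### Does a last visit that may fall from Day 90 make the crude 180-day inflammation rate, or its Kaplan-Meier check at Day 180, a flaw in the plan?

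*SAP*

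**What the plan says.** Section 5.3.1 computes the primary rate as "Total # of reported events/Total # of attempted implants x 1,000" and attaches an exact two-sided 95% interval. Section 2.2 puts every eye with an attempted implantation into the safety set, whatever its later follow-up. Section 5.1 words the endpoint as inflammation reported inside the 180 days after surgery.

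Two places show that follow-up may be shorter. Table 12-1 heads the last visit "Visit 4 & Visit 4A (Day 90 - 180 post surgery", and section 1.2 describes surveillance of eyes with a "multifocal IOL in the US (Cohort 2) for up to 180 days".

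Section 5.3.1 then adds a sensitivity check: "cumulative event rates of post-surgical intraocular inflammation (based upon the specified case definition) at 180 days will be provided using Kaplan-Meier estimator". These rates come with 95% intervals and are given separately for first, second and overall eyes. Under the first censoring rule, for an eye without inflammation, "follow-up is censored at the time (days) from each surgery to the last known date in the study for each eye". The second rule also censors event-free first eyes at second surgery, when rates for first eyes are calculated. On plots: "Graphical presentations of the Kaplan-Meier post-surgical intraocular inflammation curves for overall eyes will be included". For the secondary endpoints: "Cumulative event rates at 180 days will be provided using Kaplan-Meier estimator as described above for first eyes, second eyes, and overall eyes". Section 5.3.2 counts "All AEs occurring from when a subject signs informed consent to when a subject exits the study".

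**The concern.** A crude proportion over a fixed window is a risk estimate only if every eye is observed for the whole window. Here a fully compliant eye may finish at Day 90. Any inflammation after its last contact cannot enter the numerator, yet the eye stays in the denominator. Read as 180-day risk, the primary rate is then biased in one direction, and a larger sample would not reduce that.

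The planned Kaplan-Meier check is tabulated only at Day 180, the end of the last visit window, where the risk set may be smallest. Numbers at risk are not mentioned, and curves are planned for overall eyes only. If many late cases were missed, a post-approval safety study could report a rate that is too low, supported by a check resting on few eyes.

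**Working it through.** **1. The plan's own figure.** Section 9 gives a width of 3.6 per 1,000 at N = 3,000 and an observed rate of 2 per 1,000. That is 6 events in 3,000 eyes. The Clopper-Pearson limits are 0.73 and 4.35 per 1,000, width 3.61. The figure is reproduced.

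**2. Possible shortfall of the crude rate.** The SAP gives neither onset times nor exit days, so these are assumptions: true 180-day rate 2.0 per 1,000; share f of events after Day 90, from 0.10 to 0.50; late onset uniform over Days 90-180; exits unrelated to onset; mean exit day m. Then

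expected crude rate = 2(1 − f) + 2f(m − 90)/90.

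| Exit pattern | m | f = 0.10 | f = 0.50 |
|---|---|---|---|
| all at Day 180 | 180 | 2.00 | 2.00 |
| uniform Day 150-180 | 165 | 1.97 | 1.83 |
| uniform Day 90-180 | 135 | 1.90 | 1.50 |
| uniform Day 90-120 | 105 | 1.83 | 1.17 |
| all at Day 90 | 90 | 1.80 | 1.00 |

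With no events after Day 90 the shortfall is nil in every row. With 10% late events it is at most 2.00 − 1.80 = 0.20. The largest value, 2.00 − 1.00 = 1.00, needs half of all events to be late and every eye to leave on the first day of the window.

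**3. Whether the planned Kaplan-Meier analysis corrects it.** Simulation: 3,000 eyes, exits uniform over Days 90-180, 2,000 runs per scenario, true rate 2 per 1,000.

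| Late events | Mean crude | Mean Kaplan-Meier, Day 180 | SD crude | SD Kaplan-Meier |
|---|---|---|---|---|
| 0% | 2.01 | 2.01 | 0.83 | 0.83 |
| 25% | 1.74 | 2.03 | 0.79 | 1.42 |
| 50% | 1.48 | 1.96 | 0.70 | 1.22 |

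The estimator planned in section 5.3.1 recovers the 180-day rate on average, at the price of more variability. In 10,000 simulated studies (these three scenarios and two at 5 per 1,000) it never fell below the crude rate.

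**4. Whether a reader could see the effect.** Under uniform exits, the number at risk on day d is about 3,000 × (181 − d)/91: 3,000 at Day 90, 1,022 at Day 150, 198 at Day 175. Take six observed events, five by Day 90 and one later. The crude rate is 6/3,000 = 2.0 per 1,000 either way.

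- Late event at Day 150: 1 − (1 − 5/3,000)(1 − 1/1,022) = 2.6 per 1,000.
- Late event at Day 175: 1 − (1 − 5/3,000)(1 − 1/198) = 6.7 per 1,000.

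The gap between the two planned estimates shows how far censoring moved the result. The curve for overall eyes and the listing of all cases help to explain it.

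**5. Whether the text claims more than it delivers.** The objective in section 1.1 is to report a rate of reported inflammation, and the estimator does that. The nearest thing to a stronger claim is section 1.2, which speaks of estimating incidence; the same sentence limits follow-up to a maximum of 180 days. Section 5.2 sets no hypotheses and calls the safety analysis descriptive, so there is no threshold that a small shortfall could tip.

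**The case for a change.** The strongest counter-argument is that the check is weakest where it is tabulated. Under uniform exits only about 33 of 3,000 eyes are at risk on Day 180, and a single event there adds about 30 per 1,000. If exits cluster at Days 90-120, the Day-180 figure merely carries the curve forward flat: 2(1 − f) + 2f/3, which is 1.87 to 1.33 per 1,000 for f from 0.10 to 0.50. If no late event is observed, crude and Kaplan-Meier rates agree and the reader learns nothing about coverage. The second censoring rule thins the first-eye risk set further. Comparing a one-directional bias with the width of a random-error interval is also not quite like for like.

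All of that is arithmetically sound. What stands is that numbers at risk and a summary of follow-up per eye would make the report easier to judge. The dates needed are the ones the first censoring rule already uses, and nothing in the SAP prevents printing them.

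It does not amount to an error. Clustering at Days 90-120 is an assumption the SAP does not support, and in that case no analysis of these data could recover events in a period that nobody observed. The at-risk counts treat all eyes alike, whereas adverse events are accounted for until the subject leaves the study. A first eye in a bilateral subject may therefore have a last known date after its own Visit 4. An analysis plan's silence on at-risk rows is not a decision to omit them, since such layout is often left to table and figure shells. It is natural to suspect that the chronic category is the most exposed, but the SAP gives no onset times for any category.

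**Conclusion.** The concern does not hold. The crude rate is a valid count for the endpoint as worded, the SAP states that follow-up is up to 180 days, and unequal follow-up is addressed by the right method, at the right time point, for all eye groups and for the primary and secondary endpoints. The additions one might ask for would change no planned estimate.

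The shortfall as a 180-day risk rests wholly on assumed onset and exit times. At 2 per 1,000 it is 0 to 0.20 with 10% late events and at most 1.0 in the most extreme case tried, against a stated interval width of 3.6. That the Day-180 Kaplan-Meier rate is about unbiased assumes exits unrelated to inflammation and some eyes followed to near Day 180. Extra at-risk counts or a Day-90 row are a matter of reporting preference.

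### Does the device-precedence rule for eyes with several inflammations conflict with Kaplan-Meier censoring rule 2?

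*SAP*

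**What the plan says.** Section 5.3.1 first defines the crude primary rate as "Total # of reported events/Total # of attempted implants x 1,000". The next sentence sets the multiple-report rule, whose wording is "multiple reports of inflammation is only counted once toward the total of the inflammation cases and the one related to device will take precedence". Next, the text says that device-related inflammations will also be summarized.

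A separate paragraph introduces the sensitivity analyses: cumulative event rates "at 180 days will be provided using Kaplan-Meier estimator for first eyes, second eyes, and overall eyes". It gives two censoring rules. Rule 1 censors an eye without inflammation at its last known date. Rule 2 applies when second surgery falls within 180 days of the first. The first eye's follow-up then "will be censored at the time of second surgery, in the case of no inflammation before the second surgery". This paragraph does not mention device precedence, and it does not name the event date for an eye with several inflammations.

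For the secondary endpoints the section says: "An eye with multiple different types of inflammation is only counted once; the inflammation related to device will take precedence", followed by an order of types. It adds: "Cumulative event rates at 180 days will be provided using Kaplan-Meier estimator as described above". In the planned listing of events, "all multiple inflammations that occurred in one eye will be listed".

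**The concern.** A Kaplan-Meier estimate needs one event time per eye. The only rule in the section for choosing among several inflammations is device precedence, and that rule ignores dates. Rule 2 ignores relatedness and looks at dates.

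Take a first eye with an unrelated inflammation on Day 5, second surgery on Day 14 and a device-related inflammation on Day 75. If precedence picks the event, it falls on Day 75. Rule 2 does not censor the eye on Day 14, because inflammation came earlier. A curve meant to stop bilateral first eyes at second surgery would then contain an event after it. By Day 75 most bilateral first eyes have left the rule 2 risk set, so that one event is divided by few eyes. With events this rare, one eye could visibly move a reported sensitivity rate. The secondary curves could inherit the same question.

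**Working it through.** **The plan's own figure.** Section 9 gives a width of 3.6 per 1,000 for the exact 95% interval at N = 3,000 and a rate of 2 per 1,000. Six events in 3,000 give a Clopper-Pearson interval of 0.734 to 4.348 per 1,000, width 3.614. The figure reproduces. It does not depend on the point at issue, because an eye counts once whichever report is kept.

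**What the text asks of the example eye**

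| Reading | Event time | Consistent with the text? |
|---|---|---|
| First inflammation | Day 5 | Yes. Rule 2's condition looks at any inflammation, and the eye leaves the risk set at its first event. |
| Device-related inflammation | Day 75 | Only if a counting rule is imported into a paragraph that does not invoke it. |
| Censor at second surgery | none (Day 14) | No. Rule 2 censors only when no inflammation came before second surgery. |

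**Size if it were misread.** Inputs:

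- 3,300 eyes (Section 1.2).
- Share b of subjects with both eyes enrolled: not given, so 50, 80 and 90% are shown.
- All second surgeries by Day 60. This is an assumption suggested by the Visit 0 window in Table 12-1, "≤ 40 days pre-surgery 1st eye, ≤ 60 days pre-surgery 2nd eye".
- Full retention past Day 75 (assumed).
- First-eye cases 4, 4 and 3, about 2 per 1,000, all except the example eye occurring on Day 5 (assumed).

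First eyes: n1 = 3,300/(1 + b). Unilateral eyes: n1 × (1 − b). At risk on Day 75 under rule 2: unilateral eyes plus the example eye. With k cases:

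- dated Day 5: rate = k/n1
- dated Day 75: rate = 1 − (1 − (k − 1)/n1)(1 − 1/at risk)
- censored on Day 14: rate = (k − 1)/n1

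| b | n1 | At risk, Day 75 | Day 5 | Day 75 | Censored Day 14 |
|---|---|---|---|---|---|
| 50% | 2,200 | 1,101 | 1.82 | 2.27 | 1.36 |
| 80% | 1,833 | 368 | 2.18 | 4.35 | 1.64 |
| 90% | 1,737 | 175 | 1.73 | 6.86 | 1.15 |

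Rates are per 1,000. At 80%, for instance, 1 − (1 − 3/1,833)(1 − 1/368) = 4.35 per 1,000. The log-log Greenwood 95% intervals at 80% are 0.8 to 5.8 (Day 5) and 1.2 to 15.8 (Day 75), which overlap heavily.

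**How far this depends on the construction.** Section 2.2 also includes second surgeries more than 6 months after the first, so the Day 60 cut-off is not a fact of the plan. At 80% there are 3,300 − 1,833 = 1,467 bilateral first eyes. The example eye's own weight on Day 75 is 1/368 = 2.7 per 1,000. If 10% or 25% of second surgeries came after Day 75, it falls to 1/(368 + 147) = 1.9 or 1/(368 + 367) = 1.4. If the late case came on Day 30, with second surgeries uniform over Days 14 to 60, the weight is 1/(368 + 1,467 × 30/46) = 0.76, against 1/1,833 = 0.55 for a Day 5 date. Under rule 1 with full retention to Day 90, the choice of date makes practically no difference before then.

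**Chance that such an eye occurs.** At 2 per 1,000, 3,300 eyes give 6.6 cases, of which 6.6 × 1,467/3,300 = 2.9 fall in bilateral first eyes. The share of those with an unrelated case before and a device-related case after second surgery is not given. For assumed shares of 1, 5 and 10%, the chance of at least one is 1 − exp(−2.9 × share), about 3, 14 and 25%.

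**The case for a change.** The best case for a change is that the SAP never states the Kaplan-Meier event date, and device precedence is the only selection rule on the page. A programmer who flags one record per eye could flag the device-related one and feed it to every analysis. The secondary-endpoint sentence is more exposed: for an eye with different types it does not repeat the limitation to a total, and the Kaplan-Meier analysis follows in the same paragraph. One sentence written before the cases are known would also remove any suspicion of choosing the date afterwards.

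The omission stands as a matter of fact. It does not become a contradiction. For the primary endpoint, the precedence rule follows the crude-rate formula, is limited to the total of cases, and leads into the summary of device-related inflammations. It decides how a case is classified, not when it began. For the secondary endpoints the wording is looser. Because the curves are a sensitivity analysis of the type-specific rates, the sensible reading is that an eye enters the curve of the type it is counted under. The planned listing shows every inflammation in such an eye, so a reader can see which date was used.

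**Conclusion.** This is missing detail that an analyst fills sensibly. Section 5.3.1 does not contradict itself: precedence governs counting and classification, while both censoring rules turn on whether the eye had any inflammation. Time to first inflammation satisfies rule 2 and ordinary Kaplan-Meier practice, and in the example it gives 2.18 per 1,000 at an 80% bilateral share, equal to the crude 4/1,833. The value 4.35 requires importing the counting rule, and 1.64 requires breaching rule 2's stated condition.

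Those figures rest on one constructed eye, an assumed bilateral share, and a late case placed after every assumed second surgery; milder assumptions shrink the effect considerably. The affected output is mainly the rule 2 first-eye rate, a descriptive sensitivity analysis in a study with no formal safety hypotheses (Section 5.2). The primary crude rate and its exact interval are the same under every reading. No change to the plan is needed.

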#### 9 SAMPLE SIZE AND POWER CALCULATIONS

The precision of the estimated rate can be assessed using the width of an exact two-sided 95% confidence interval. In Figure 9-1, the exact two-sided 95% confidence intervals with a sample size (N) of 3,000 are shown when the observed rate ranges from 1 to 10 (per 1,000).

As an example, with N=3,000, the width of the exact two-sided 95% confidence interval will be 3.6 (per 1,000) when the observed rate is 2 (per 1,000).

Figure 9-1 The exact two-sided 95% confidence intervals with N=3,000 when the observed rate ranges from 1 to 10 (per 1,000)

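### Kaplan-Meier censoring at each eye's last date inflates the Day-180 rate for any case first found, and dated, at Visit 4

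*SAP*

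**What the plan says.** Cases are gathered as "all reported cases of post-surgical intraocular inflammation over 4 visits ranging from 1 to 180 days post implantation" (SAP section 1.2). The last scheduled column before unscheduled visits in Table 12-1 is "Visit 4 & Visit 4A (Day 90 - 180 post surgery", a 90-day window.

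The primary rate in section 5.3.1 is crude: "Total # of reported events/Total # of attempted implants x 1,000". As a sensitivity analysis, cumulative rates "at 180 days will be provided using Kaplan-Meier estimator for first eyes, second eyes, and overall eyes" are planned. Under rule 1, for an eye without inflammation, "follow-up is censored at the time (days) from each surgery to the last known date in the study for each eye". The secondary endpoints inherit the method: "Cumulative event rates at 180 days will be provided using Kaplan-Meier estimator as described above".

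The SAP does not say whether the Kaplan-Meier event time is the onset date or the date of detection. It does not treat Visit 4 as one interval, and it does not carry eyes that complete Visit 4 forward to Day 180.

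**The concern.** Visit 4 is both the last scheduled examination and, normally, the end of follow-up. An eye seen and clear on Day 100 leaves the risk set on Day 100. An eye found inflamed at its Visit 4 on Day 165, and dated there, is divided only by the eyes whose Visit 4 has not yet taken place. Kaplan-Meier treats those eyes as known to be clear on Day 165, although their last scheduled examination was Visit 3 (Day 30 to 60). Leaving the risk set is thus tied to having been examined and found clear, so censoring is not independent of the recorded event time.

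These curves are planned for the primary endpoint and all four secondary endpoints, and they are the plan's check on incomplete follow-up. A Kaplan-Meier rate well above the crude rate could be read as late risk that the crude rate misses, when it only reflects the Visit 4 date of one or two eyes.

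**Working it through.** **Inputs from the SAP.** Rule 1 and the Day-180 reading (section 5.3.1); the Visit 4 window of Day 90 to 180 (Table 12-1); N = 3,000 from section 9, where "the exact two-sided 95% confidence intervals with a sample size (N) of 3,000 are shown".

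**The plan's own figure.** Six events in 3,000 eyes (2 per 1,000) give an exact interval of 0.734 to 4.348 per 1,000. The width is 3.61, which reproduces the stated 3.6.

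**Assumptions (not in the SAP).** Visit 4 falls evenly on the 91 whole days from Day 90 to Day 180. Late onset is uniform over Days 60 to 180. The share of late cases dated at Visit 4 is varied.

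**Step 1: weight of one Visit 4 case.** The estimator is 1 − Π(1 − d/n), where n is the number of eyes still at risk. On day t the share of eyes still at risk is (181 − t)/91, so a case dated on day t is weighted 91/(181 − t) relative to the crude rate. One case is 1,000/3,000 = 0.33 per 1,000 in the crude rate.

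| Visit 4 day | Weight | Adds per 1,000 |
|---|---|---|
| 90 | 1.0 | 0.33 |
| 120 | 1.5 | 0.50 |
| 135 | 2.0 | 0.66 |
| 150 | 2.9 | 0.98 |
| 165 | 5.7 | 1.9 |

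At the middle visit date half of the eyes remain, so the median weight is about 2 (simulated 1.9, quartiles 1.3 to 3.7). The mean over the 91 days is 1 + 1/2 + … + 1/91 = 5.1. The simulated median stays at 1.9 to 2.0 for early-, mid- and late-weighted visit dates. It falls to 1.2 if half of the eyes share one exit day and to 1.0 if all do.

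**Step 2: effect on the reported rate.** Take 5 early cases (5/3,000 = 1.67 per 1,000) and a late risk of 0.5 per 1,000, so the true Day-180 risk is 2.17. A late case has arisen by a Visit 4 on day v with probability (v − 60)/120.
- Put j = 181 − v. The mean multiplier on late risk for cases dated at Visit 4 is the sum over j = 1 to 91 of (121 − j)/(120j) = (121/120) × 5.094 − 91/120 = 4.38.
- For cases dated at onset the multiplier is about 1.
- If a share p of late cases is dated at Visit 4, the mean is about 1.67 + 0.5 × [4.38p + (1 − p)].

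| Share p | Formula | Simulated mean | Simulated median |
|---|---|---|---|
| 1 | 3.86 | 3.8 to 3.9 | about 2.3 |
| 0.5 | 3.01 | 3.0 | about 2.05 |
| 0 | 2.17 | 2.15 to 2.17 | about 2.0 |

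For a type that arises only late, with true risk 1.0 per 1,000 and p = 1, the formula gives a mean of 4.38 (simulated 4.2 to 4.4; median about 2.0).

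**Step 3: the alternatives on the same inputs.** The average Visit 4 is Day 135, so a late case has arisen by Visit 4 with probability (135 − 60)/120 = 0.625. A visit-interval estimate with no dropout is then 1.67 + 0.5 × 0.625 = 1.98 (simulated 1.97) against 2.17, and 0.63 against 1.0 for the late-only type. Dating cases at the midpoint between the last clear examination and the detecting visit gives 2.01 and about 0.70.

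**The case against.** The strongest reply is that the SAP fixes no event date. The case definition lies outside this document, and event dating may be settled there too. Table 12-1 has an unscheduled-visit column covering adverse events, symptoms, slit-lamp findings and culture, so a late case can present between visits and carry its own onset date. Kaplan-Meier handles such a case properly. This stands, and it makes the size conditional. It does not remove the point, because the censoring rule is fixed and gives a wrong Day-180 rate for any case first found at Visit 4 with no documented earlier onset.

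For a bilateral subject, the first eye's last date might be read as the subject's last date, after Visit 4A. With second surgery assumed 7 to 30 days after the first, the median weight over all eyes falls to about 1.5. The inflation is smaller but remains.

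The stakes are limited. There are no hypotheses, the analysis is a sensitivity analysis, every event is listed by eye so an odd late step can be traced, and the error overstates risk. All of this stands.

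A reader might infer that reported Kaplan-Meier rates will typically double. The documents do not support that: twofold is the median weight of one Visit 4 case. With six cases, one of them found at Visit 4, the median estimate is 2.35 against a crude 2.0. Nor do they show that chronic endophthalmitis must be worst affected, which would require those cases to wait for Visit 4.

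**Conclusion.** The point holds in conditional form and is worth correcting. Rule 1, read with the Visit 4 window, overweights cases first found at Visit 4 and dated there: about twofold at the median and fivefold on average for a single case if visit dates are spread evenly. The effect on the whole rate depends on how many late cases are so dated. In the scenario above the mean runs from about 2.2 (none) through 3.0 (half) to 3.8 (all), against a true 2.17. Even with all late cases dated at Visit 4 the median is only about 2.3, so the mean is driven by occasional very late visits. The visit dates, late risk and detection shares are assumptions, not figures from the SAP.

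Only the Kaplan-Meier sensitivity analyses of the primary and secondary endpoints are affected. It would be wrong to infer that the primary result is biased by this rule: the crude rate and its exact interval do not use it.

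**What to change.** Amend the sensitivity-analysis text in SAP section 5.3.1; the secondary endpoints follow by its cross-reference. State that:

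1. an event is dated at its documented onset where one exists;
2. for cases first found at a scheduled visit, the cumulative rate is estimated by visit interval (through Visits 1, 2, 3 and 4);
3. every eye assessed at Visit 4 stays in the denominator for the whole last interval, and only eyes leaving before Visit 4 are censored early;
4. the result is labelled as risk through Visit 4 (Day 90 to 180).

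The cost is a few sentences and minor programming, with no new data. The downside is that cases arising after an early Visit 4 get no credit, so the estimate lies close to the crude rate (about 1.97 against 2.17, and about 0.63 against 1.0 for a late-only type). The label in item 4 makes that explicit.

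Midpoint dating of visit-detected cases is an acceptable alternative that keeps the Day-180 reading. It understates a late-only type by about 30% (about 0.7 against 1.0), still far nearer than the mean of about 4.2 when such cases are dated at Visit 4 under rule 1.
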